5.3 Exclusion criteria

Patients eligible for this study must not meet **any** of the following criteria:

1. Patient with symptomatic visceral disease or any disease burden that makes the patient ineligible for endocrine therapy per the investigator's best judgment.
2. Patient has received prior treatment with chemotherapy (except for neoadjuvant/ adjuvant chemotherapy), fulvestrant, any PI3K, mTOR or AKT inhibitor
3. Patient has a known hypersensitivity to alpelisib or fulvestrant, or to any of the excipients of alpelisib or fulvestrant.
4. Patient with inflammatory breast cancer at screening.
5. Patient is concurrently using other anti-cancer therapy.
6. Patient has had surgery within 14 days prior to starting study drug or has not recovered from major side effects.
7. Patient has not recovered from all toxicities related to prior anticancer therapies to NCI CTCAE version 4.03 Grade ≤ 1 . Exception to this criterion: patients with any grade of alopecia are allowed to enter the study.
8. Patients with Child pugh score B or C.

9. Patient has received radiotherapy \leq 4 weeks or limited field radiation for palliation \leq 2 weeks prior to randomization, and who has not recovered to grade 1 or better from related side effects of such therapy (with the exception of alopecia) and/or from whom \geq 25% of the bone marrow was irradiated.
10. Patient has a concurrent malignancy or malignancy within 3 years of randomization, with the exception of adequately treated, basal or squamous cell carcinoma, non-melanomatous skin cancer or curatively resected cervical cancer.
11. Patient has central nervous system (CNS) involvement
If patient is fulfilling the following 3 criteria she/he is eligible for the trial.
 - completed prior therapy (including radiation and/or surgery) for CNS metastases \geq 28 days prior to the start of study and
 - Central Nervous System (CNS) tumor is clinically stable at the time of screening and
 - patient is not receiving steroids and/or enzyme inducing anti-epileptic medications for brain metastases
12. Patients with an established diagnosis of diabetes mellitus type I or not controlled type II (based on FPG and HbA1c, see inclusion criterion 12)
13. Patient has impairment of gastrointestinal (GI) function or GI disease that may significantly alter the absorption of the study drugs (e.g., ulcerative diseases, uncontrolled nausea, vomiting, diarrhea, malabsorption syndrome, or small bowel resection)
14. Patient has a known history of Human Immunodeficiency Virus (HIV) infection (testing not mandatory)
15. Patient has any other concurrent severe and/or uncontrolled medical condition that would, in the investigator's judgment, contraindicate patient participation in the clinical study (e.g. chronic active hepatitis, severe hepatic impairment, etc.)
16. Patient has currently documented pneumonitis (chest CT scan performed at baseline for the purpose of tumor assessment should be reviewed to confirm that there are no relevant pulmonary complications present).
17. Patient has clinically significant, uncontrolled heart disease and/or recent cardiac events including any of the following:
 - History of angina pectoris, coronary artery bypass graft (CABG), symptomatic pericarditis, or myocardial infarction within 12 months prior to the start of study treatment
 - History of documented congestive heart failure (New York Heart Association functional classification III-IV)
 - Documented cardiomyopathy
 - Patient has a Left Ventricular Ejection Fraction (LVEF) $<$ 50% as determined by MUGA scan or ECHO
 - History of any cardiac arrhythmias, (e.g. ventricular tachycardia), complete left bundle branch block, high grade AV block (e.g. bifascicular block, Mobitz type II and third degree AV block), supraventricular, nodal arrhythmias, or conduction abnormality in the previous 12 months.

- Uncontrolled hypertension defined by a Systolic Blood Pressure (SBP) \geq 160 mmHg and/or Diastolic Blood Pressure (DBP) \geq 100 mm Hg, with or without anti-hypertensive medication. Initiation or adjustment of antihypertensive medication(s) is allowed prior to screening.
- Long QT syndrome, family history of idiopathic sudden death or congenital long QT syndrome, or any of the following:
 - Risk factors for Torsades de Pointe (TdP) including uncorrected hypokalemia or hypomagnesemia, history of cardiac failure, or history of clinically significant/symptomatic bradycardia
 - Concomitant medication(s) with a known risk to prolong the QT interval and/or known to cause TdP that cannot be discontinued or replaced by safe alternative medication
 - Bradycardia (heart rate $<$ 50 at rest), by ECG or pulse.
 - On screening, inability to determine the QTcF interval on the ECG (i.e.: unreadable or not interpretable) or corrected QT (QTcF) $>$ 450 msec for males and $>$ 460 msec for females (using Fridericia's correction). All as determined by screening ECG (mean of triplicate ECGs).

18. Patient is currently receiving any of the following medications and cannot be discontinued 7 days prior to the start of the treatment:

- That have a known risk to prolong the QT interval or induce TdP.
- Herbal preparations/medications

19. Patient is currently receiving or has received systemic corticosteroids \leq 2 weeks prior to starting study drug, or who have not fully recovered from side effects of such treatment.

Note: The following uses of corticosteroids are permitted: single doses, topical applications (e.g. for rash), inhaled sprays (e.g. for obstructive airways diseases), eye drops or local injections (e.g. intra-articular).

20. Sexually active males unless they are sterilized (at least 6 months prior to screening) or use a condom during intercourse while taking drug and for at least 8 months after stopping alpelisib and/or Fulvestrant medication and should not father a child in this period. A condom is required to be used also by vasectomized men in order to prevent delivery of the drug via seminal fluid.

21. Participation in a prior investigational study within 30 days prior to the start of study treatment or within 5 half-lives of the investigational product, whichever is longer.

22. Not able to understand and to comply with study instructions and requirements.

23. History of acute pancreatitis within 1 year of screening or past medical history of chronic pancreatitis

24. Patient who relapsed with documented evidence of progression more than 12 months from completion of (neo)adjuvant endocrine therapy with no treatment for metastatic disease

6 Treatment

6.1 Study treatment

For this study, the term “investigational drug” refers to Novartis study drug alpelisib. Fulvestrant is also being used in this study. Study treatment in this study refers to the combination of drugs in each of the study arms and includes alpelisib/placebo and fulvestrant. This is a double blind placebo controlled study, the investigator and patient will be blinded (i.e. will not know if the patient is receiving alpelisib or placebo). The storage conditions for the alpelisib/placebo will be described on the medication label.

Novartis Drug Supply Management or its designee will provide alpelisib and placebo as 50 mg and 200 mg tablets as individual patient supply, packaged in bottles. Alpelisib will be dosed on a flat scale of mg/day and not be adjusted to body weight or body surface area.

Fulvestrant will be procured locally according to local practice and regulation, or supplied by Novartis (or its designee). Storage conditions are described in the medication label. Medication labels will comply with the legal requirements of each country and be printed in the local language.

All dosages prescribed and dispensed to the patient and all dose changes during the study must be recorded on the Dosage Administration Record Case Report Form (CRF).

6.1.1 Dosing regimen

All eligible patients will be randomized to receive either:

- Alpelisib 300 mg p.o. + fulvestrant 500 mg i.m. or
- Alpelisib Placebo 300 mg p.o. + fulvestrant 500 mg i.m.

During randomized treatment phase, alpelisib 300 mg or alpelisib matching placebo will be administered orally once daily on a continuous dosing schedule starting on Cycle 1 Day 1 in combination with fulvestrant 500 mg starting on Cycle 1 Day 1 and 15 and Day 1 of every cycle thereafter (+/- 3 days) in a 28 days cycle. Treatment crossover from fulvestrant plus placebo to fulvestrant plus alpelisib will not be permitted in this study.

A complete cycle of treatment is defined as 28 days (\pm 3 days) of once daily continuous treatment of alpelisib or placebo in combination with fulvestrant.

The last day of a complete treatment cycle is Day 28. Day 1 of the next cycle starts on Day 29.

All dosages prescribed and dispensed to the patient and all dose changes during the study must be recorded on the Dosage Administration Record CRF.

Table 6-1 Alpelisib/placebo and fulvestrant dose and treatment schedule

Study drugs	Pharmaceutical form and route of administration	Dose ²	Frequency and/or Regimen
Alpelisib/placebo	Film coated tablet for oral use	300 mg (e.g. 2 x 50 mg tablets+1x200 mg tablet ¹)	Daily (continuous) starting C1D1
Fulvestrant	Injection for i.m. administration	500 mg	Days 1, 15 on Cycle 1 and Day 1 at each cycle thereafter

¹ In case of patient supply difficulties, any combination of alpelisib/placebo (according to patient assignment) may be taken to consume the total dose.

² Dose reduction levels for alpelisib/placebo will be administered accordingly. For example, alpelisib/placebo 250mg should preferentially be administered as 1 X 50 mg tablets + 1 x 200 mg tablet

6.1.1.1 Alpelisib/placebo dosing

Alpelisib at a dose of 300 mg or placebo will be administered orally once daily on a continuous dosing schedule starting on Cycle 1 day 1 in combination with fulvestrant 500 mg intra muscular at day of randomization.

Alpelisib/placebo is dosed on a flat scale of mg/day and not by weight or body surface area. The maximum recommended daily dose of alpelisib/ placebo is 300 mg.

There will be no breaks between dosing cycles.

The investigator or responsible site personnel should instruct the patient to take the study drugs as per protocol (promote compliance). Drug accountability must be performed on a regular basis. Patients will be instructed to return unused study drugs to the site at the end of each cycle. The site personnel will ensure that the appropriate dose of each study drug is administered at each visit and will provide the patient with the correct amount of drugs for subsequent dosing.

The following general guidelines should be followed for alpelisib/placebo administration:

- Patients should be instructed to take the dose of alpelisib/placebo once daily at approximately the same time each day immediately after a meal (preferably in the morning after breakfast) except on the days blood collection is scheduled at the clinic, at which time the patients should take their doses at the clinic at any later point of time.
- Alpelisib/placebo must be taken immediately after a meal or snack. If, for any reason, a breakfast (or other meal) was not consumed, then the patient should take study treatment with a glass of water immediately after a snack. If this happens on days of PK sampling, it should be documented in the CRF.
- If a dose of alpelisib/alpelisib matching-placebo is missed, it can be taken immediately after food and within 9 hours after the time it is usually administered. After more than 9 hours, the dose should be skipped for that day. On the next day, alpelisib/placebo should be taken at the usual time.
- Alpelisib/placebo should be taken with a glass of water. Patients should swallow the tablet as a whole and not chew or crush them.
- During treatment phase, the patient should record if the dose was taken or not in the alpelisib/placebo patient diary.

- If the patient vomits after taking the alpelisib/alpelisib matching-placebo dose, the patient should not take an additional dose on that day and should resume the usual dosing schedule the next day at the usual time.
- The occurrence and frequency of any vomiting during a treatment cycle must be noted in the adverse events section of the CRF.

6.1.1.1.1 Additional dosing guidelines for pharmacokinetic sampling

On days with pharmacokinetic sampling

- For sparse PK subset: Cycle 1 Days 8 and 15, Cycle 2, 4, 6, 8 Day1
- For trough PK: Cycle 2, 4, 6, 8 Day 1

The following additional guidelines should be followed:

The pre-dose sample should be drawn before alpelisib/placebo dosing. On days and time points when PK, biochemistry, hematology or other blood samples are to be performed, the PK sample must be drawn first. The sampling time of the pre-dose PK sample and the dosing time of alpelisib/placebo must be precisely recorded in the CRF. Furthermore, the dosing time of alpelisib/placebo on the previous day must be precisely recorded in the CRF and in the alpelisib/placebo patient diary. If vomiting occurs, the exact time of the first vomiting episode within the first 4 hours post-dosing on that day must be noted. Time of administration of gastric protection agents on days of PK sampling should be precisely recorded in the CRF.

6.1.1.1.2 Additional dosing guidelines for fasting glucose and/or amylase/lipase and/or c-peptide and/or lipid profile sampling

On days with a pre-dose fasting (overnight) glucose and/or amylase/lipase and/or c-peptide and/or lipid profile samples as described in [Table 7-1](#) and [Section 7.2.2.5.3](#) the following additional guidelines should be followed:

The patient must be fasting overnight for 8-12 hours prior to the blood collection, but can freely drink water. After this blood sample, the patient should have a light breakfast. Alpelisib/placebo must be taken within 1 hour after the meal in the clinic. If a pharmacokinetic sample is also being drawn, then the sample should be taken before alpelisib/placebo dosing, as described in [Section 7.2.3](#).

6.1.1.2 Fulvestrant dosing

Fulvestrant 500 mg will be given at Cycle 1 Day 1 and 15 after randomization and then at Day 1 of each subsequent cycle during the randomized treatment phase (+/- 3 days). Fulvestrant is administered intramuscularly into the buttocks slowly as two 5mL injections, one in each buttock.

No dose modification is allowed for fulvestrant. Please refer to the local approved prescribing information. Any planned variance from these guidelines in the view of the patient safety must be previously discussed with the Sponsor unless there is an urgent need for action.

6.1.1.2.1 Additional dosing guidelines for pharmacokinetic sampling

On days with fulvestrant pharmacokinetic sampling (Day 15 of Cycles 1, 2, 4, 6, and 8) the following additional guidelines should be followed: the pre-dose sample should be drawn just before fulvestrant dosing. The sampling time of the pre-dose PK sample and the dosing time of fulvestrant must be precisely recorded in the CRF. Furthermore, the dosing date and time of the previous dose of fulvestrant must be precisely recorded in the CRF.

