7.2.3.2 Fulvestrant pharmacokinetic blood sampling schedules

The fulvestrant plasma concentration will be collected in order to assess the impact of alpelisib on fulvestrant exposure in approximately 200 patients (same population as for alpelisib sparse PK assessment). Fulvestrant is administered once monthly after the first cycle and steady state is fully reached after 6 administrations. Pre-dose plasma concentrations will be collected during this period and two cycles after ([Table 7-6](#)) in order to assess the time course to reach steady-state.

In trough patients a single fulvestrant pre-dose sample will be taken at steady state at Cycle 6 Day 1 ([Table 7-6](#)).

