1	15	Pre-dose*	302 3021	302	2	401 4011	401	2
1	15	1 h post dose ± 10 min	302	303	2			
1	15	2 h post dose ± 30 min	302	304	2			
1	15	4 h post dose ± 30 min	302	305	2			
1	15	6 h post dose ± 30 min	302	306	2			
1	15	8 h post dose ± 30 min	302	307	2			
2	1	Pre-dose*	303 3031	308	2	402 4021	402	2
4	1	Pre-dose*	304 3041	309	2	403 4031	403	2
6	1	Pre-dose*	305 3051	310	2	404 4041	404	2
8	1	Pre-dose*	306 3061	311	2	405 4051	405	2
Anytime		Unscheduled		3001+	2		4001+	2

* Take sample immediately prior to study treatment dose; at days of PK evaluation oral treatment doses should be taken at the clinical site

+ Refer to Lab manual for naming conventions

§ Four digit dose reference ID for pre-dose and 24h post dose samples ending on 1 refers to the dose taken before the PK sample (last dose information)

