2.1.6 Last date of exposure to study drug/treatment

The study treatment schedule is organized in cycles of 28 days.

The **last date of exposure to study treatment** is derived to be the latest date of the last date of exposure to alpelisib/placebo and fulvestrant. The last date of exposure to alpelisib/placebo and last date of exposure to fulvestrant will be derived as follows.

Alpelisib/placebo is administered daily on a continuous once daily dosing schedule. Hence, the **last date of exposure to alpelisib/placebo** is the date of last administration of alpelisib/placebo.

Fulvestrant is administered on

- Cycle 1 Day 1
- Cycle 1 Day 15, and
- The first day of every cycle thereafter (e.g. Cycle 2 Day 1, Cycle 3 Day 1 etc.)

Due to the irregularly spaced fulvestrant dose administration, the **last date of exposure to fulvestrant** is calculated using a different method depending on the cycle at which fulvestrant was discontinued:

1. If the patient discontinues fulvestrant between Cycle 1 Day 1 and Cycle 1 Day 14 inclusive:
 - The last date of exposure to fulvestrant is calculated as (last date of administration of fulvestrant) + (length of time interval to next scheduled dose - 1) i.e. [last date of fulvestrant administration+ (14-1)].
 - If the patient died or was lost to follow-up within last date of administration of fulvestrant + 13 days, the last date of exposure to fulvestrant is the date of death or the date of last contact, respectively.
2. If the patient discontinues fulvestrant between Cycle 1 Day 15 and Cycle 2 Day 1:
 - The last date of exposure to fulvestrant is calculated as (last date of administration of fulvestrant) + (length of time interval - 1) i.e. [last date of fulvestrant administration+ (14-1)].
 - If the patient died or was lost to follow-up within last date of administration of fulvestrant + 13 days, the last date of exposure to fulvestrant is the date of death or the date of last contact, respectively.
3. If the patient discontinues fulvestrant on or after Cycle 2 Day 1, then:

- the last date of exposure to fulvestrant is calculated as (last date of administration of fulvestrant) + (length of time interval - 1) i.e. [last date of fulvestrant administration+(28-1)].
- If the patient died or was lost to follow-up within last date of administration of fulvestrant + 27 days, the last date of exposure to fulvestrant is the date of death or the date of last contact, respectively.

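### Protocol 6.1.1.2.1 lists four fulvestrant pre-dose PK days on which no fulvestrant is given, against the dosing text and Tables 7-6 and 7-7 (secondary PK only)

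*Protocol*

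**What the plan says.** **Sampling instruction.** Protocol 6.1.1.2.1 begins "On days with fulvestrant pharmacokinetic sampling (Day 15 of Cycles 1, 2, 4, 6, and 8" and then requires that "the pre-dose sample should be drawn just before fulvestrant dosing".

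**Dosing.** Protocol 6.1.1.2 states "Fulvestrant 500 mg will be given at Cycle 1 Day 1 and 15 after randomization and then at Day 1 of each subsequent cycle", with a window of 3 days either side. Table 6-1 gives the same schedule: "Days 1, 15 on Cycle 1 and Day 1 at each cycle thereafter". SAP 2.1.6 lists Cycle 1 Days 1 and 15 and then "The first day of every cycle thereafter (e.g. Cycle 2 Day 1, Cycle 3 Day 1 etc".

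**PK logs.** Table 7-7 (sparse subset, about 200 patients) has five scheduled fulvestrant rows: Cycle 1 Day 15, then Day 1 of Cycles 2, 4, 6 and 8. For all other patients, section 7.2.3.2 says "a single fulvestrant pre-dose sample will be taken at steady state at Cycle 6 Day 1", and Table 7-6 agrees.

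**Use of the samples.** Protocol 1.2.4.2 and 10.5.5.1 plan to compare fulvestrant pre-dose concentrations between arms, with and without alpelisib, and to describe the time course to steady state. Characterizing fulvestrant PK is a secondary objective in the protocol summary.

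**Analysis rule.** SAP 3.10.1 applies one pre-dose definition to both drugs: before the dose on the assessment day, and about 24 ± 2 hours after the last dose. The steady-state criteria that follow it are written for alpelisib only.

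**The concern.** A pre-dose sample is a trough only if a dose follows it. After Cycle 1, Day 15 falls halfway between two fulvestrant injections, so the instruction in 6.1.1.2.1 cannot be carried out as written. A site that kept to the listed days would draw a mid-interval sample. If such samples were summarized with true troughs, the between-arm fulvestrant comparison and the description of the approach to steady state would mix two different quantities.

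This is current, operative text and a direct instruction to sites. The parallel section for alpelisib, 6.1.1.1.1, is worded correctly (Cycle 1 Days 8 and 15, then Day 1 of Cycles 2, 4, 6 and 8 for the sparse subset). A dropped reference to Day 1 is therefore the likely cause, but the parenthesis as printed has no other reading.

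**Working it through.** **1. Listed days against tabled days.** Cycles are 28 days, so study day = (cycle − 1) × 28 + cycle day.

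| Cycle | Listed in 6.1.1.2.1 | Table 7-7 | Gap (days) | Planned dose on listed day? | Planned doses either side |
|---|---|---|---|---|---|
| 1 | Day 15 = study day 15 | Day 15 = 15 | 0 | yes | n/a |
| 2 | Day 15 = 28 + 15 = 43 | Day 1 = 29 | 14 | no | 29 and 57 |
| 4 | Day 15 = 84 + 15 = 99 | Day 1 = 85 | 14 | no | 85 and 113 |
| 6 | Day 15 = 140 + 15 = 155 | Day 1 = 141 | 14 | no | 141 and 169 |
| 8 | Day 15 = 196 + 15 = 211 | Day 1 = 197 | 14 | no | 197 and 225 |

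One of five agrees. Each of the other four lies 14 days after one planned dose and 14 days before the next.

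**2. Can a visit window close the gap?** The dosing window is ±3 days. The PK window is ±1 day, and sparse samples have none beyond Table 7-7 (sections 7.1 and 7.2.3.3.1). Together these give at most 4 days, against a gap of 14.

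**3. Where could a wrong draw happen?** Table 7-1 shows Day 15 visits in Cycles 1 and 2 and only Day 1 visits afterwards. Of the four conflicting days, only Cycle 2 Day 15 coincides with a scheduled visit.

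**4. How different would a mid-interval value be?** The documents give no ratio of a Day 15 value to a trough. Section 1.2.1.1 gives a ratio of more than 2 between mean Cmax and Cmin at steady state, a peak at about 5 days, and a terminal half-life of 40 to 50 days. Two illustrations, both resting on assumed log-linear decline:

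- Terminal half-life alone, over the 14 days to the trough: 2^(14/50) = 1.21 to 2^(14/40) = 1.27.
- A fall of exactly 2-fold from day 5 to day 28 (23 days): 2^(14/23) = 1.5.

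The half-life alone gives only 2^(23/50) = 1.38 to 2^(23/40) = 1.49 from day 5 to day 28, short of the stated 2-fold. The first illustration is therefore probably low. The second would rise if the true peak-to-trough ratio exceeds 2, but would stay below that ratio.

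**5. Would the SAP filter remove such a sample?** Under SAP 3.10.1 a pre-dose sample must fall 22 to 26 hours after the last dose. A correctly timed fulvestrant sample follows the previous dose by 14 × 24 = 336 hours (Cycle 1 Day 15 and Cycle 2 Day 1) or 28 × 24 = 672 hours (Day 1 of Cycles 4, 6 and 8). Read literally, the rule drops every correct fulvestrant trough. With the 24-hour part ignored for fulvestrant, the remaining condition would remove a Day 15 sample in later cycles, because no dose follows it that day. The SAP does not say which reading applies.

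**The case against.** The strongest reply is that the controlling schedule is clear. Table 7-1 sends sites to Tables 7-6 and 7-7 for PK time points. Every scheduled fulvestrant row there falls on a dosing day, and no sample number exists for Day 15 of Cycles 2, 4, 6 or 8 except under the unscheduled entry. SAP 3.10.1 already asks for samples before dosing on the assessment day, SAP 3.10.5 lets invalid concentrations be flagged and left out of summaries, and the protocol requires the sample time and the previous dose date and time in the CRF. Enrollment ended on 21 July 2017 and the current protocol is dated 11 February 2020. A patient starting on that last enrollment date would reach study day 211 in February 2018, so planned fulvestrant sampling was over about two years earlier.

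Most of this stands, and it limits the consequence. Two gaps remain. Section 7.2.3.2 refers the sparse patients' serial sampling to Table 7-6, which holds only the Cycle 6 Day 1 fulvestrant row; their schedule is in Table 7-7. And the SAP filter does not work for fulvestrant as written.

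A reader might infer more than the documents support:

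- That four of five samples in about 200 patients were mistimed. Four of five counts the conflicting days; no mistimed sample is shown.
- That the error is about 2-fold. That ratio compares the peak, near day 5, with the trough. Day 15 lies between them.
- That the comparison is biased towards one arm. Sites are blinded to treatment (section 6.5.3), so a misreading would be expected in both arms and would mainly add noise.
- That the whole drug-interaction assessment is at risk. The trough comparison covers alpelisib's effect on fulvestrant; the reverse direction uses population PK (section 1.2.4.2).

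**Conclusion.** The contradiction is real and confined to secondary PK. Of the five days in 6.1.1.2.1, only Cycle 1 Day 15 is both a fulvestrant dosing day and a tabled sampling day. The other four are 14 days later than the tabled samples and carry no dose. The plausible practical error is an extra or misplaced draw at Cycle 2 Day 15. Its size cannot be fixed from the documents: the illustrations run from about 1.2 to 1.5 times the trough, assuming log-linear decline and a peak-to-trough ratio of exactly 2 in the second case. How many samples, if any, were drawn on the wrong day is not stated. No primary or key secondary analysis depends on them. The point is an internal inconsistency in the sampling schedule and implies nothing about dosing.

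**What to change.** 1. Reconcile the sampling days in Protocol 6.1.1.2.1 with Tables 7-6 and 7-7, and correct the table reference in 7.2.3.2 for the sparse subset. Check the laboratory manual, which is not among the documents, for the same wording. Cost: a sentence in each place. Since planned sampling is over, this mainly corrects the record.
2. Check recorded fulvestrant sample dates and times against recorded fulvestrant dose dates, and list any sample not followed by a dose that day. The CRF fields already exist, so this is one data check.
3. In SAP 3.10.1, give fulvestrant its own pre-dose rule: the sample was taken before a fulvestrant dose given on that day. State that the 24 ± 2 hour condition applies to alpelisib only. Samples failing the fulvestrant rule stay in the listings but leave the time-point summaries and the between-arm comparison. Cost: one sentence and a small programming change.
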